Note that Addendum #1 provides for enrollment of subjects after adenotonsillectomy at or prior to study visit 2. This allows increased opportunity for interested families who are not able to schedule the pre-operative visit or who are referred to the study after their surgery to participate in this research. More information on this additional study arm is provided in the addendum and the MOP.

**C3. Procedures.** Each participant will undergo a baseline, pre-randomization evaluation of sleep and neurobehavioral variables at 4 months after AT, as several months are required to ensure complete healing. Most of the neurobehavioral benefit achieved after AT for SDB accrues in the first 3 months (unpublished data from the investigators). After baseline assessments, all subjects will be randomized to CPAP or non-CPAP (standard care) groups. Group assignments will be made using a randomization algorithm, possibly with automatic adjustment that prospectively ensures balance between groups for SDB status, residual post-operative SDB symptoms, gender, age and/or BMI. Non-CPAP families will be contacted by the program manager for 6 months at intervals designed to replicate the frequency and nature of investigator contacts in the CPAP group. Discussion will focus on recuperation after AT, general health, and any suggestion of serious adverse effects that would warrant discontinuation of study participation and referral for clinical evaluation. These end-points would include recommendations by a child's pediatrician or otolaryngologist to pursue this option; development of a new, serious cardiopulmonary condition that makes prompt assessment and treatment for any residual SDB imperative; or emergence of serious academic or developmental concerns in the setting of obvious, persistent symptoms of SDB. Each questionable case will be brought by the program manager to the PI (section 6.5) for a decision and possible notification of the DSMB per the Data and Safety Management Plan guidelines.

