**Behavioral Assessments:** Standardized rating scales to be completed by a child's parent or guardian will include the Conners' Parent Rating Scales (CPRS-R:L) and the Child Behavior Checklist (CBCL), with the primary study outcome measure, Behavioral Index, being constructed from the sum of the T-scores from the Conners' ADHD Index and CBCL Attention Deficit/Hyperactivity Problems. Parents also will complete the CPRS-R:L and CBCL at the pre-operative meeting after signing the consent materials with their child. Although not representing a primary outcome point for this study, this assessment will serve to familiarize parents with the process of observational reporting on their child; provide important information or grouping variables for secondary analyses; and help to confirm that CPAP and control groups have equivalent behavior at baseline. Because of the importance consistently reported for the measurement of executive functioning in children with SDB, the Behavior Rating Inventory of Executive Functioning (BRIEF) also will be completed. Finally, quality of life will be measured from both the Peds-QL parent and child forms. The CPRS-R:L, CBCL, and BRIEF are available in teacher forms that will allow secondary, corroborative assessment in both a home and school environment, and help address any evident parental bias. Through experience in our laboratory and work with the multicenter Childhood Adenotonsillectomy (CHAT) trial, for which our center directs quality assurance and monitoring of behavioral and cognitive assessments, we have developed techniques to sustain strong return rates for teacher ratings.

Any or all survey instruments used in this study may be administered as paper forms or electronic versions, which may be delivered by email or via a web-based software system such as Qualtrics, or as a combination of paper and pencil and electronic formats, depending on the form type and the reporter (child, parent or teacher). *Any instrument for survey over the internet will be or is being developed through the auspices of the computer*

*support group in Psychiatry and MCIT to be sure it is HIPPA compliant, as are current measures employed in Psychiatry for their patient metrics.*

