##### **(a) Primary Outcome Measure:**

1. Neurobehavioral change (hypothesis 2c CPAP vs controls intent to treat)

Change in **behavioral index** following 6 months of CPAP vs. no CPAP use by children after AT

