### **(c) Exploratory Outcome Measures:**

Measures of academic achievement, fluid cognition, and REREC are all considered exploratory.

C8. Analyses. For Hypothesis 1a, post-AT SDB as an outcome variable will be defined as a respiratory disturbance index (RDI)  $\geq 1$  obstructive or mixed apnea, hypopnea, or respiratory effort-related arousal per hour of sleep. The 22-item SDB scale score (on a continuous scale from 0.0 to 1.0^43) will provide the main explanatory variable. Logistic regression models will be assessed for sensitivity to potential covariates or confounds, including age, gender, race, body mass index z-score, and socioeconomic status. Secondary analyses will focus on RDI as a continuous outcome; validated snoring, sleepiness, and behavior subscales within the SDB scale; habitual snoring as a single, previously informative question-item; and most importantly SDB data generated by innovative algorithms, as described above, exploratory analyses for RCREC, esophageal pressures, and sleep dynamics. For Hypothesis 1b, multiple linear regression models will be constructed to assess cross-sectional associations between each neurobehavioral morbidity (the Behavioral Index being the primary outcome) and the SDB questionnaire score or RDI as the main explanatory variable. Models of the SDB questionnaire will use a slightly shortened, 16-item version (as previously) to exclude behavioral questions that would correlate with outcome measures for artificial reasons. Covariates as above will be taken into account. Secondary analyses will 1) assess the impact of SDB scores or RDI on other behavioral and cognitive measures; 2) take IQ and achievement into account within the main models; and 3) test the 3 newer, computed SDB measures in place of RDI. To assess Hypothesis 2a, the investigators will define adequate adherence as at least 4 hours of electronically recorded CPAP use per night, on average over the most recent 3 months on treatment. A series of multiple linear regression models will be used, with post-CPAP improvement in neurobehavioral variables as outcomes. The pre-CPAP SDB questionnaire scores or RDI will serve as the main explanatory variables. Secondary analyses will use the 3 SDB measures generated by computer algorithms as the explanatory variables. To assess Hypothesis 2b, the same outcomes will be regressed on CPAP adherent vs. non-adherent categorization, as well as (secondarily) a continuous measure of adherence as defined by mean hours of nightly use during the last 3 months of the trial. As with Hypotheses 1a and 1b, models for 2a and 2b also will be assessed after adjustment for similar potential covariates or confounds. To assess Hypothesis 2c, intent-to-treat analyses will use models that regress each primary neurobehavioral outcome on initial CPAP vs. control group assignment, after adjustment for BMI z-scores, age,

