
gender, race, and socioeconomic status. Exploratory models will in addition consider RDI (or computer algorithm proxy measures) and PSQ scores at 4 or 10 months post-AT, to assess whether residual SDB on these measures may explain differences in neurobehavioral outcomes. Exploratory analyses will also compare outcomes between CPAP-adherent subjects and controls, to assess (by contrast to the primary intent-to-treat analysis) what benefit may be lost by poor adherence, cross-overs, or drop outs.

In addition to standard SAS and Excel databases, REDCap (Research Electronic Data Capture) may be used for database development and data capture and management on this study as well as in tracking study activity. REDCap is a web-based electronic data capture system available under contract to the University of Michigan. Developed by Vanderbilt University, with collaboration from a consortium of institutional partners, REDCap provides a secure, web-based application designed to support data capture for research studies. REDCap is endorsed by the Michigan Institute for Clinical and Health Research (MICHR) and is part of larger data collection initiatives under the CTSA grant. REDCap was developed specifically around HIPAA-Security guidelines and has been disseminated for use locally at other institutions. By mid-2011, REDCap was being used by more than 200 academic/nonprofit consortium partners on six continents supporting more than 20,000 research end-users ([www.project-redcap.org](http://www.project-redcap.org)).

At the University of Michigan, the application is restricted to users on the UMHS Internal Network requiring a secure connection to communicate with U-M services i.e. VPN. The database is stored on a server separate from the application. Servers are maintained and supported by the Medical School Information Services (MSIS). REDCap Application support and services are provided by the Michigan Institute for Clinical and Health Research (MICHR).

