**C9. Sample Size.** Plans are based on extensive preliminary data from the investigators on effects of AT for childhood SDB, and on the only quantitative preliminary data published, in 2009, for the neurobehavioral effects of CPAP in children with obstructive sleep apnea. Data from our group (section C9.3) show that the proportion of children, among those who undergo AT here for SDB, who have residual SDB 6 months later is about 50% or more, depending on criteria used to define SDB. Children with mildest SDB can have robust improvement in behavior, as measured with particular relevance for the current application on the Conners' ADHD Index. This improvement, by 0.5 standard deviations, is at least as strong as the that observed in more severe apneics. Yet, more than 0.5 standard deviations still separate Connors' scores in post-AT SDB patients from those in controls. The CPAP intervention we propose is a gold-standard widely believed to completely remedy any residual airway obstruction in adherent subjects. The CPAP may well, therefore, prove to be a more definitive treatment than AT in final elimination of even mild SDB. In a study of 21 children aged 6 to 16 years, with SDB of any severity and unselected for neurobehavioral problems, 3 months of CPAP was associated with robust improvement in inattention and hyperactivity on the Conners' scale ( $p<.001$  despite the limited sample) and in subjective sleepiness (Epworth,  $p<.001$ ). Adherence with PAP correlated with improvement in the Conners' measure ( $r=.48$ ,  $p=.03$ ) and the Epworth ( $r=.58$ ,  $p=.006$ ). These results emerged despite use of PAP by the subjects on only 56% of all nights on average. Our preliminary data (C9.7) suggest that we can expect about 67% our subjects to show adequate adherence.

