Given these observations, we anticipate conservatively that a sample of 80 CPAP subjects who complete the protocol will contain about 40 with SDB ( $RDI>1$ ); that 53 will be adherent with PAP; and that most subjects with  $RDI>1$  along with some subjects who have  $RDI<1$  (but perhaps SDB symptoms) will benefit from PAP. For hypothesis 1a, to test for a correlation between SDB questionnaire scores and polysomnographically-defined SDB, we will have 80% power to detect a clinically meaningful Spearman correlation  $\rho \geq 0.25$  with  $\alpha=.05$ . Similarly, for hypothesis 1b, which focuses on an association between residual neurobehavioral problems and either SDB questionnaire scores or RDI, we will be able to detect a  $\rho \geq 0.25$ . For hypothesis 2a, with about 27 post-AT, CPAP-adherent subjects who have  $RDI>1$  and 26 who have  $RDI<1$ , we will have 82% power to reject the null hypothesis (that the mean 6-month change scores in the Behavioral Index for the two groups are equal) if the effect size is  $\geq 0.8$ . The likelihood of this result is based on observations in our previous studies with the Conners' ADHD Index, which is a main component of the Behavioral Index now proposed. Based on improvement we have measured in the past after AT for children with mildest levels of SDB, for the current hypothesis 2b, in which we will compare about 53 treated (adherent) to 27 non-treated (non-adherent) residual apneics, we should have power of 0.78 to detect an effect size  $\geq 0.65$ . This effect size is substantially smaller than that implied by the correlations above among 21 children and by our own preliminary data below. For

*hypothesis 2c, comparison of 80 CPAP-treated subjects to 40 controls should provide 80% power to detect a Behavioral Index difference between groups (effect size)  $\geq 0.55$ . The 120 subjects will be recruited from the 2,475 children aged 5-12 years anticipated to have AT at the two otolaryngology practices during 3 years and 4 months of study enrollment. In each of two previous R01 studies here that followed children for 12 or 6 months after AT, attrition was only 5% with careful attention to each family from an experienced project manager. The study now proposed will conservatively anticipate 10% attrition, and target enrollment of 132 subjects.*

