Contact will be made with subjects before AT (as opposed to 4 months later) for two reasons. First, the investigators would like to minimize decisions not to participate simply because good improvement in symptoms are seen after AT. Although every family will have the right to withdraw at any time from the research, the investigators believe that even children who improve after AT may well improve further with definitive treatment for any residual SDB. Second, the visit just before AT will allow the investigators to administer simple but important questionnaires that will assess SDB symptoms and neurobehavioral morbidity at baseline, before any major intervention in most cases. This could provide important opportunities to explore selection bias at study entry; adjust statistical models for SDB or neurobehavioral problem severity at entry; compare gains from AT to those from subsequent PAP; and perhaps gain insight into what symptoms prior to AT may predict ultimate need for post-surgical PAP that provides additional benefit. Further, this visit will include a very brief cognitive assessment that will give young children experience with a one-on-one testing experience to reduce subsequent novelty and improve reliability. However, an addendum to this protocol also allows enrollment after the child's adenotonsillectomy (at or before study visit 2) for families who are not able to schedule a preoperative study visit due to time constraints at the time of the initial referral, or because they were referred only after the surgery. This will allow more opportunities for participation of eligible children who would otherwise have enrolled preoperatively.

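### The primary intent-to-treat model (H2c) leaves out the pre-randomisation Behavioral Index as a covariate; adding it would usually sharpen the comparison at almost no cost

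*Combined protocol and SAP*

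**What the plan says.** C7(a) names one primary outcome, "Neurobehavioral change (hypothesis 2c CPAP vs controls intent to treat"), which is the change in Behavioral Index over six months with CPAP versus without. C8 gives the H2c analysis as "models that regress each primary neurobehavioral outcome on initial CPAP vs. control group assignment, after adjustment for BMI z-scores, age", "gender, race, and socioeconomic status". The exploratory H2c models that follow add RDI and PSQ scores.

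C3 provides the baseline: "Each participant will undergo a baseline, pre-randomization evaluation of sleep and neurobehavioral variables at 4 months after AT". The same section has a parent complete the behavioural rating scales during that testing. The SV2 Behavioral Index is therefore planned for every child before allocation.

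Two other places touch on baseline behaviour, and both concern the earlier ratings taken before surgery. C5 says these will "provide important information or grouping variables for secondary analyses". Section 6.1.a says the pre-operative visit could make it possible to "adjust statistical models for SDB or neurobehavioral problem severity at entry". Neither is carried into the H2c model. Children enrolled after surgery under the addendum may have no pre-operative ratings.

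C9 states 80% power for H2c with 80 CPAP and 40 control children at an effect size of 0.55.

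**The concern.** Baseline is usually the strongest single predictor of a follow-up score. The H2c model adjusts for five background variables but uses the outcome's own baseline only by subtracting it. Subtraction assumes a slope of exactly 1 on the SV2 score. If the true slope is lower, as it is with equal SDs and any correlation below 1, the change score carries avoidable noise.

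H2c is the sole primary outcome, its planned power has no margin at 0.55, and no interim analysis is anticipated. The Behavioral Index is also not among the factors that the randomisation might balance (C3). Protection against chance imbalance in baseline behaviour is the same gain in precision seen from another side, so it should not be counted twice.

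**Working it through.** **Inputs from the documents.** 80 versus 40 children, effect size 0.55, 80% power (C9); change in Behavioral Index as outcome (C7); five covariates (C8). C9 gives an alpha of 0.05 beside H1a only; two-sided 0.05 is assumed for H2c.

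**Inputs the documents do not give.** The SV2–SV4 correlation r, the ratio k = SD(SV4)/SD(SV2), and the units of the 0.55. Ranges are assumed.

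**Reproducing the plan's figure.** The noncentrality is 0.55/√(1/80 + 1/40) = 2.84. A two-sided noncentral t test on 118 df gives power 0.804; one-sided would give 0.881. The stated 80% is therefore a two-sided comparison without baseline adjustment. With df reduced for five covariates (113) it is still 0.804.

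**Effect of adding SV2.** Set SD(SV2) = 1 and SD(SV4) = k.

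- Variance of the change score: 1 + k² − 2rk
- Residual variance with SV2 in the model: k²(1 − r²)
- The first minus the second is (1 − rk)², which is never negative and is zero only when rk = 1.

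With k = 1 the ratio of the second to the first is (1 + r)/2. Power with SV2 uses an effect of 0.55/√((1 + r)/2) on 112 df, with 0.55 read in SDs of change:

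| r | variance ratio | 95% CI narrower by | power without SV2 | power with SV2 | same precision as unadjusted N |
|---|---|---|---|---|---|
| 0.5 | 0.75 | 13.4% | 0.804 | 0.902 | 120/0.75 = 160 |
| 0.7 | 0.85 | 7.8% | 0.804 | 0.863 | 120/0.85 = 141 |
| 0.8 | 0.90 | 5.1% | 0.804 | 0.843 | 120/0.90 = 133 |
| 0.9 | 0.95 | 2.5% | 0.804 | 0.824 | 120/0.95 = 126 |

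**If 0.55 is in SDs of the score (k = 1).** The standardised effect is 0.55/√(2(1 − r)) without SV2 and 0.55/√(1 − r²) with it. Power is 0.804 v 0.902 at r = 0.5, 0.953 v 0.976 at r = 0.7 and 0.994 v 0.997 at r = 0.8. At r = 0.3 it is 0.663 v 0.839, but that row does not fit the plan's stated 80%.

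**Unequal SDs.** Reduction in residual variance at r = 0.5/0.7/0.8/0.9:

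- k = 0.9: 33%/25%/21%/19%
- k = 1.1: 18%/8%/3%/0%
- k = 1.25: 11%/2%/0%/5%

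**With the five covariates in both models.** Simulation used 10,000 trials per setting, five normal covariates with coefficient 0.2 on both scores, k = 1, and 0.55 in change SDs. Power without and with SV2 was 78.6% v 88.6%, 78.1% v 84.4%, 79.0% v 82.8% and 79.2% v 80.8% at the same four r. The gains are about 10, 6, 4 and 2 points.

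**Cost where nothing is gained.** At r = 0.8 and k = 1.25 (rk = 1), 40,000 simulated trials gave 78.7% without SV2 and 78.4% with it, a cost of about 0.3 point.

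**The case against.** The planned analysis is sound. A change score and a baseline-adjusted model are both valid in a randomised comparison, and the stated power reproduces without the covariate. This stands, and it is why the point concerns efficiency and not error.

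The size of the benefit rests wholly on r, k and the units of 0.55, none of which the documents supply. Depending on those, the gain can be about 10 points of power or nothing. This also stands: the algebra and the omission are certain, the gain in this trial is not. The largest apparent gain, at r = 0.3 on the score-SD reading, should carry little weight, because it implies 66% power for the planned test where the plan states 80%.

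C8 does not repeat the word change for H2c; that reading comes from C7 and from the wording C8 uses for H2a. It is an inference. If the SV4 score itself were modelled without SV2, the omission would cost more: adding SV2 would multiply the variance by 1 − r², which is 0.75 at r = 0.5 and 0.36 at r = 0.8.

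The authors did think about baseline behaviour, in C5 and 6.1.a. Those passages concern the pre-operative ratings, are secondary or optional, and do not put SV2 into the H2c model.

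**Conclusion.** The concern holds. The SV2 Behavioral Index is planned for every child before randomisation, yet no passage makes it a covariate in the primary model. Apart from one degree of freedom, the adjusted model is never less precise in large samples.

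Under equal SDs and r between 0.5 and 0.9, the confidence interval would be about 13% to 2.5% narrower. With the five planned covariates in both models, power would be about 10 to 2 points higher if 0.55 is in SDs of change. If it is in SDs of the score, the gain is about 10 points at r = 0.5, 2 points at r = 0.7 and under 1 point from r = 0.8 upward. The gain disappears near rk = 1.

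The units matter and C9 leaves them open. It argues partly in score SDs ("more than 0.5 standard deviations still separate" post-surgery patients from controls on the Conners' scale), frames H2a in change ("that the mean 6-month change scores in the Behavioral Index for the two groups are equal"), and for H2c says only effect size.

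**What to change.** In C8, state the H2c primary model as the SV4 Behavioral Index (or its change from SV2) regressed on arm, SV2 Behavioral Index, BMI z-score, age, gender, race and socioeconomic status. Once SV2 is in the model, the two forms give the same treatment estimate, which also settles whether change or the raw score is meant. In C9, say whether 0.55 is in SDs of change or SDs of the score.

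Optionally, use the same form for the secondary H2c outcomes (NIH Toolbox, Epworth, MSLT, PedsQL), each with its own SV2 value. The documents give no power basis for these, so no gain is claimed for them.

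The cost is one line in C8, a few words in C9 and one degree of freedom. At the zero-gain point it is about 0.3 point of power. No child is lost from the analysis, since anyone with a change score already has an SV2 value. Fixing the model in advance also removes any later choice between adjusted and unadjusted results.

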**Aim 2:** *Randomize Aim 1 subjects to receive 6 months of standard clinical care (control group,  $n=40$ ) vs. CPAP titration (CPAP group,  $n=80$ ), home use of CPAP, and monitored adherence; and then re-assess all subjects with all baseline sleep and neurobehavioral tests.*

**H2a:** Among CPAP subjects who have adhered to the therapy, residual questionnaire or polysomnographic evidence of SDB from 4 months post-AT, as compared to no residual SDB, will predict greater improvement 10 months post-AT in hyperactive behavior, attention deficit, and sleepiness.

**H2b:** Among all CPAP subjects ( $n=80$ ), neurobehavioral outcomes will improve more, from baseline to follow-up, among subjects who adhere successfully to CPAP than among those who do not.

**H2c:** *Among all subjects ( $n=120$ ), neurobehavioral outcomes will improve more among CPAP subjects than control subjects in an intent-to-treat analysis.*

**Impact:** Results will demonstrate the clinical utility of an SDB questionnaire and polysomnography after AT; implicate post-AT residual SDB as a potential cause of persistent neurobehavioral problems; and suggest that successful treatment of post-AT SDB provides tangible clinical benefits.

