- d) Failure to reinitiate CPAP therapy after a period off-treatment due to an upper respiratory illness or other interfering event.

The number and frequency of visits will depend on: (1) the child's current threshold; and (2) how the child and family advance through each step of the desensitization protocol. The decision to hold on a particular step of the desensitization program will be based on whether the homework was completed and/or whether the child's current level of anxiety or opposition is elevated. A recommendation to discontinue CPAP treatment may be made if the child or family has not progressed to another step in 2-4 weeks (depending on the number of visits during that time). Discontinuation of PAP treatment may occur after case consultation with other members of the study team to insure that all strategies have been considered. Additional effort to improve adherence is not desirable because this would not resemble practice available at most other clinical centers. In addition, varying levels of adherence will be necessary to test hypothesis 2b.

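### H2b and the adherent-versus-control comparison condition on post-randomisation adherence, so either can show a difference when CPAP does nothing; label them associational and add a complier analysis with stated assumptions

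*Combined protocol and SAP*

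**What the plan says.** C8 defines adequate adherence as an average of at least 4 electronically recorded hours of CPAP per night over the latest 3 months of treatment. For H2b, "the same outcomes will be regressed on CPAP adherent vs. non-adherent categorization"; mean nightly hours over the last 3 months of the trial is a secondary continuous version. H2b supplies secondary outcomes 5 to 9 in C7(b). For H2c, C8 plans intent-to-treat models and then says: "Exploratory analyses will also compare outcomes between CPAP-adherent subjects and controls". The stated purpose is to see how much benefit poor adherence, cross-over and drop-out cost.

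The covariates named in C8 are age, gender, race, BMI z-score and socioeconomic status; H2a and H2b are to use similar ones. No measure of baseline behaviour or family engagement is named. Section 6.1.a mentions adjustment for severity at entry only as a possibility.

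C3 describes desensitisation for children who struggle with CPAP. Whether a step is held depends on homework completion and on "whether the child's current level of anxiety or opposition is elevated". Lack of progress may lead, after case consultation, to a recommendation to stop.

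C9 describes H2b as a comparison "in which we will compare about 53 treated (adherent) to 27 non-treated (non-adherent) residual apneics". The Aim 2 impact statement expects results to "suggest that successful treatment of post-AT SDB provides tangible clinical benefits".

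**The concern.** Randomisation balances the CPAP and control arms. It does not balance children who adhere against children who do not, or adherers against an unselected control arm. The primary outcome is parent-rated attention and hyperactivity behaviour (C5), and children with Attention Deficit/Hyperactivity Disorder, Conduct Disorder or Oppositional Defiant Disorder are eligible (C2). If behaviour or family engagement helps decide who reaches 4 hours, adherence carries prognostic information about the outcome itself.

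What is at stake is interpretation. C9 calls the two H2b groups treated and non-treated. C10.7 uses an adherent versus non-adherent contrast to argue that CPAP probably caused improvement, while conceding that the comparison group is imperfect. A positive H2b could be read in the same way. The gap between the adherent-versus-control result and the intent-to-treat result could likewise be read as benefit lost to non-adherence when part of it is selection.

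**Working it through.** **Inputs.** From C9: 80 CPAP and 40 control children; 53 adherent and 27 non-adherent, so 53/80 = 0.6625 (C9 puts expected adherence at about 67%). Outcome SD is set to 1. From neither document: the strength and direction of selection into adherence. These are assumed and varied.

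**The plan's own figures.** For H2b, C9 says "we should have power of 0.78 to detect an effect size" of at least 0.65.
- SE = sqrt(1/53 + 1/27) = 0.236. Power = Φ(0.65/0.236 − 1.96) = 0.785; the noncentral t gives 0.775. The stated 0.78 is reproduced with two-sided alpha 0.05.
- H2c at 0.55: SE = sqrt(1/80 + 1/40) = 0.194. Power is 0.811 (z) or 0.804 (t), against a stated 80%.

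**Bias with no CPAP effect.** Suppose the kind of child who adheres would improve δ SD more than other children in either arm.
- H2b bias = δ.
- Adherent-versus-control bias = (1 − 0.67) × δ, because about 67% of controls are the same kind of child.
- H2b rejection ≈ Φ(δ/0.236 − 1.96); the simulated values below are close to this.

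| Assumed δ | H2b false difference | H2b rejection (simulated) | Adherent v control |
|---|---|---|---|
| 0.2 | 0.20 | about 13% | 0.07 |
| 0.3 | 0.30 | about 24% | 0.10 |
| 0.5 | 0.50 | about 54% | 0.17 |

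A second model gives the same picture. Let a latent trait that determines adherence have correlation ρ with outcome change. H2b bias is then ρ × 0.365 × (1/0.6625 + 1/0.3375) = 1.63ρ, where 0.365 is the normal density at the adherence cut. At ρ = 0.4 this is 0.65 SD, the whole effect H2b is powered for. Intent-to-treat rejection stays near 5% throughout.

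**Sign.** At ρ = −0.3 the H2b bias is −0.49 SD. If difficult behaviour only raises the baseline score, regression to the mean in change scores gives −0.10 to −0.22 SD, against CPAP (assumed baseline/follow-up correlation 0.6-0.8; severity/adherence correlation 0.2-0.3).

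**Complier average causal effect.** Estimate = intent-to-treat difference ÷ difference in the proportion treated.
- Under the selection scenarios above with no CPAP effect, it averages about 0. With a true 0.5 SD effect in adherers it averages 0.50, while H2b averages 0.70-1.00 for δ of 0.2-0.5.
- SE = 0.194/0.6625 = 0.29, against sqrt(1/53 + 1/40) = 0.21 for adherent-versus-control.
- A direct effect of open-label assignment of 0.1 or 0.2 SD, with no CPAP effect, gives 0.1/0.6625 = 0.15 or 0.2/0.6625 = 0.30.
- If adherers gain 0.40 and sub-threshold users 0.20, the 4-hour version gives (0.6625 × 0.40 + 0.3375 × 0.20)/0.6625 = 0.50, not 0.40.

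**Total error of the two comparisons, no CPAP effect.** Root mean squared error for adherent-versus-control is sqrt(bias² + 0.21²) = 0.22, 0.23 and 0.27 at δ = 0.2, 0.3 and 0.5. For the complier estimate it is 0.29-0.30.

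**The case against.** The plan already protects its main conclusion: intent-to-treat is primary, the adherent-versus-control contrast is labelled exploratory and set against it, the Aim 2 impact wording is hedged and covers all three hypotheses, and the section A summary defers proof of causation to a later multicentre trial. H2b analyses change, so a stable behavioural difference cancels. The covariate list is open-ended. All of this stands, and it keeps the point below a threat to the primary result. It does not supply a caveat on H2b or commit the plan to a behavioural covariate.

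Three stronger readings are tempting and unsupported.
- A reader might infer that C3 classes oppositional children as non-adherent. It does not. Adherence is defined by recorded hours alone; homework and opposition govern desensitisation steps. The link to adherence class is a reasonable inference, no more.
- A reader might infer that the bias must favour CPAP. The documents do not establish a direction, and plausible mechanisms run both ways.
- A reader might infer that the randomised arms yield an unbiased effect of adherence that should replace the exploratory comparison. Randomisation alone yields intent-to-treat. The complier estimate also requires that assignment act only through PAP use. That is doubtful here: the trial is unblinded, the outcome is parent-rated, and CPAP families may receive behavioural support not described for controls, although control contacts are meant to match in frequency and nature. Its total error also exceeds that of the planned comparison across the range examined. Addition is justified; replacement is not.

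**Conclusion.** The concern holds as one of interpretation and of a missing analysis. H2b and the adherent-versus-control comparison are non-randomised contrasts on a post-randomisation variable, and the named covariates leave the likely confounders uncovered. H2b is much the more exposed: its bias equals the assumed adherer advantage, while the exploratory comparison takes about one third of it. Every magnitude rests on that assumed advantage, so the figures show what could happen, not what will. H2c is not affected. A complier analysis would bring the randomisation to bear on the effect in children who use CPAP, but only under an exclusion assumption that cannot be tested, and with limited precision: a 95% half-width of 1.96 × 0.29 = 0.57 SD.

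**What to change.** Amend C8 as follows.

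1. Keep the adherent-versus-control comparison. Beside it, add a complier average causal effect by two-stage least squares, with randomised arm as instrument and the H2c covariates. Treatment received is the 4-hour adherence class. A further version uses mean nightly PAP hours; it assumes a linear dose effect and is read per hour. Count PAP that controls report obtaining outside the study as received.
2. State the assumption that assignment acts only through PAP use, and say that it is doubtful under open-label, parent-rated assessment and can fail for sub-threshold users. Report a sensitivity analysis over a direct assignment effect of at least 0.1-0.2 SD.
3. Add the study visit 2 Behavioral Index to the H2b and adherent-versus-control models. This addresses baseline severity and regression to the mean, not selection on later course. Label both contrasts associational.
4. State that the Aim 2 conclusion on benefit of treatment rests on H2c, supported by the complier estimate.

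The cost is protocol wording, one model and a sensitivity table. Arm, recorded hours in the CPAP arm and outcomes are already collected. Outside PAP use by controls needs a question at the scheduled contacts and would be parent-reported, which A4 notes tends to overstate use. The downside is a wider interval for the binary-class estimate (SE about 0.29 v 0.21 SD; this figure does not apply to the hours version) and reliance on the exclusion assumption.
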